| Dienogest and ethinylestradiol | G03AA16 |
| Progestogens and oestrogens, sequential preparations | |
| Megestrol and oestrogen | G03AB01 |
| Lynestrenol and oestrogen | G03AB02 |
| Levonorgestrel and oestrogen | G03AB03 |
| Norethisterone and oestrogen | G03AB04 |
| Desogestrel and oestrogen | G03AB05 |
| Gestodene and oestrogen | G03AB06 |
| Chlormadinone and oestrogen | G03AB07 |
| Dienogest and oestrogen | G03AB08 |
| Progestogens | |
| Norethisterone | G03AC01 |
| Lynestrenol | G03AC02 |
| Levonorgestrel | G03AC03 |
| Quingestanol | G03AC04 |
| Megestrol | G03AC05 |
| Medroxyprogesterone | G03AC06 |

| | |
|----------------|---------|
| Norgestrienone | G03AC07 |
| Etonogestrel | G03AC08 |
| Desogestrel | G03AC09 |

NOTE: emergency contraceptives (ATC G03AD) are not included.

Table 16.2 Gemscript codes to identify hormonal contraceptives in THIN

| Gemscript | Descriptor |
|---|---|
| first & later first generation | |
| 90566998 | Ethinylestradiol with norethisterone - biphasic 7 x 35mcg+500mcg; 14 x 35mcg+1mg Tablet |
| 90703997 | Ethinylestradiol with norethisterone - triphasic 7 x 35+500mcg; 7 x 35+750mcg; 7 x 35mcg+1mg Tablet |
| 90703998 | Ethinylestradiol with norethisterone - triphasic 7x35+500mcg; 9x35mcg+1mg; 5x35+500mcg Tablet |
| 92682998 | Mestranol with norethisterone Tablet |
| 93280992 | ETHINYLLOESTRADIOL 50MCG/ETHYNODIOL 1MG MCG TAB |
| 93334992 | ETHINYLLOESTRADIOL 30MCG/ETHYNODIOL 2MG MCG TAB |
| 94158996 | Ethinylestradiol 30microgram / Norethisterone acetate 1.5mg tablets |
| 94158997 | Ethinylestradiol 20microgram / Norethisterone acetate 1mg tablets |
| 94408992 | ANOVLAR 21 TAB |
| 94994992 | ETHINYLLOESTRAD. 50MCG/NORETHISTERONE 3MG MCG TAB |
| 94995992 | ETHINYLLOESTRADIOL/NORETHISTERONE 35 MCG TAB |
| 95289992 | MINOVLAR TAB |
| 95338992 | NORLESTRIN TAB |
| 95885998 | Mestranol 50microgram / Norethisterone 1mg tablets |
| 97470998 | Ethinylestradiol with norethisterone and placebo 50mcg + 1mg Tablet |
| 97472998 | Ethinylestradiol with norethisterone acetate 50mcg + 1mg Tablet |
| 97474998 | Ethinylestradiol with norethisterone acetate 50micrograms + 3mg Tablet |
| 97476998 | Ethinylestradiol with norethisterone acetate 50micrograms + 3mg Tablet |
| 97563998 | Generic Synphase tablets |
| 98085997 | Ethinylestradiol 35microgram / Norethisterone 1mg tablets |
| 98085998 | Ethinylestradiol 35microgram / Norethisterone 500microgram tablets |

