| 98170998 | LEVONORGESTREL 30mcg tablets |
| 98172998 | Norethisterone 350mcg tablet |
| 98174998 | Norethisterone 350mcg tablet |
| Ring | |
| 83186998 | Ethinylestradiol 2.7mg / Etonogestrel 11.7mg vaginal delivery system |
| 84617998 | Ethinylestradiol 2.7mg / Etonogestrel 11.7mg vaginal delivery system |
| Patches | |
| 89295998 | Norelgestromin with ethinylestradiol 203micrograms + 33.9micrograms/24hours Transdermal patch |
| 91878998 | Ethinylestradiol 33.9micrograms/24hours / Norelgestromin 203micrograms/24hours transdermal patches |
| 94918998 | ETHINYL+NOREL 600mcg/6mg patch |
| Injections Progestogens | |
| Gemsript codes | |
| 85241998 | MEDROXYPROGEST 150mg/1mL inj |
| 85242998 | Medroxyprogesterone 150mg/1ml suspension for injection pre-filled syringes |
| 94485998 | Medroxyprogesterone acetate 80mg/ml Oral suspension |
| 94789998 | Medroxyprogesterone acetate 80mg/ml Oral suspension |
| 95700998 | Norethisterone 200mg/1ml solution for injection ampoules |
| 97454998 | NORETHISTERONE 200mg/1mL inj |
| 97920998 | MEDROXYPROGEST 150mg/1mL inj |
| 97921998 | MEDROXYPROGEST 50mg/mL inj |
| Read Codes | |
| 61B..00 | Depot contraceptive |

| | |
|-----------------------------|---|
| 61B..11 | Depot contraception |
| 61B1.00 | Depot contraceptive given |
| 61B1.11 | Depo-provera injection given |
| 61B2.00 | Depot contraceptive repeated |
| 61B3.00 | Depot contraceptive-no problem |
| 61B4.00 | Depot contraceptive - problem |
| 61B5.00 | Depot contraception stopped |
| 61BZ.00 | Depot contraceptive NOS |
| Implant Progestogens | |
| Read Codes | |
| 61K..00 | Subcutaneous contraceptive |
| 61KA.00 | Insertion of subcutaneous contraceptive |
| 61KB.00 | Check of subcutaneous contraceptive |
| 61KD.00 | Subcutaneous contraceptive in situ |
| 61KE.00 | Subcut contraceptive implnt palp |
| 61KZ.00 | Subcutaneous contraceptive NOS |
| 7G2AB00 | Insertion of subcutaneous contraceptive |
| 7G2H700 | Removal of subcutaneous contraceptive |
| 9m7..00 | Contraceptive implant removal invitation |
| 7G2AA00 | Insertion of Norplant |
| 7G2H500 | Removal of Norplant |
| Gemscript | |
| 81886998 | ETONOGESTREL 68mg implant |
| 90908998 | Etonogestrel 68mg implant |
| 90909998 | ETONOGESTREL 68mg implant |
| 92888998 | LEVONORGESTREL 38mg implant |
| 98222998 | Levonorgestrel 228mg Implant |
| LNGIUSs | |
| Read | |
| 615S.00 | Mirena coil check |
| 7E09500 | Removal of Mirena coil |
| 7E09400 | Introduction of Mirena coil |
| Gemscript | |

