| 97118997 | Erythromycin 500mg ec gastro-resistant tablets |
| 97121990 | Doxycycline 100mg capsules |
| 97209989 | Doxycycline 100mg capsules |
| 97246992 | Doxycycline 100mg capsules |
| 97361997 | Erythromycin stear 500mg tabs |
| 97381992 | Erythromycin stear 500mg tabs |
| 97559997 | Minocycline 100mg tablets |
| 97559998 | Minocycline 50mg tablets |
| 97738989 | Minocycline 100mg tablets |
| 97738990 | Minocycline 50mg tablets |
| 97761989 | Doxycycline 100mg capsules |
| 97913998 | Doxycycline 100mg tablets |
| 98029989 | Minocycline 100mg tablets |
| 98029990 | Minocycline 50mg tablets |
| 98044990 | Doxycycline 100mg capsules |

| | |
|----------|--|
| 98166989 | Erythromycin 500mg ec gastro-resistant tablets |
| 98231998 | Doxycycline 100mg disp tabs |
| 98345990 | Erythromycin 500mg ec gastro-resistant tablets |
| 98352990 | Doxycycline 100mg capsules |
| 98480989 | Minocycline 100mg tablets |
| 98530998 | Minocycline 100mg m/r capsules |
| 98531996 | Minocycline 100mg capsules |
| 98531997 | Minocycline 50mg capsules |
| 98531998 | Minocycline 100mg modified-release capsules |
| 98558990 | Erythromycin 500mg ec gastro-resistant tablets |
| 98601989 | Doxycycline 100mg capsules |
| 98751997 | Erythromycin 500mg/sach grans |
| 98752998 | Erythromycin 500mg e/c tablet |
| 98754998 | Erythromycin stear 500mg tabs |
| 98969997 | Doxycycline 100mg disp tabs |
| 98969998 | Doxycycline 100mg capsules |
| 99054998 | Lymecycline 408mg capsules |
| 99101998 | Doxycycline 100mg capsules |
| 99103996 | Erythromycin 500mg e/c tablet |
| 99210990 | Erythromycin 500mg ec gastro-resistant tablets |
| 99433990 | Erythromycin 500mg ec gastro-resistant tablets |
| 99434990 | Erythromycin 500mg ec gastro-resistant tablets |
| 99435989 | Erythromycin 500mg ec gastro-resistant tablets |
| 99542997 | Erythromycin stear 500mg tabs |
| 99613990 | Doxycycline 100mg capsules |
| 99683997 | Erythromycin 500mg e/c tablet |

Table 16.5 Codes of diagnoses of hyperandrogenic conditions during the year before index date for PHARMO and HSD

| Diagnosis* | ICD-10 | ICD-9(-CM) | ICPC |
|-----------------------------|------------------|---|------------------|
| Acne | L70 | 706.0, 706.1 | S96 |
| Alopecia | L63-L66 | 704.0 | S23 |
| Contraceptive management | Z30.01 | V25.01, V25.02, V25.05 | W11-W12 |
| Hirsutism | L68.0 | 704.1,757.4 (incl. sub code 59 for HSD) | S24.01 |
| Menstrual problems | N92, N94.3-N94.9 | 626.1, 626.2, 626.4, 626.8, 626.9 | X02-X03, X06-X09 |

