| Oligomenorrhoea/amenorrhoea | N91 | 626.0, 626.1 | X05 |
| PCOS | E28.2 | 256.4 | T99.06 |
| Seborrhoea | L21 | 706.3 | S86 |

*all diagnoses will be based on episode text mining in GP episodes as well; PCOS = polycystic ovary syndrome.

Table 16.6 Read codes of diagnoses of hyperandrogenic conditions or conditions EE/progestin combinations are prescribed for frequently during the year before index date for THIN

| Read code | Descriptor |
|--------------------------|---------------------------------|
| Acne | |
| 2FG5.00 | Acne scar |
| M153000 | Acne rosacea |
| M26..00 | Sebaceous gland diseases |
| M260.00 | Acne varioliformis |
| M260000 | Acne frontalis |
| M260z00 | Acne varioliformis NOS |
| M261.00 | Other acne |
| M261000 | Acne vulgaris |
| M261100 | Acne conglobata |
| M261600 | Cystic acne |
| M261A00 | Pustular acne |
| M261E00 | Acne excoriee des jeunes filles |
| M261F00 | Acne fulminans |
| M261X00 | Acne, unspecified |
| M261z00 | Other acne NOS |
| Myu6800 | [X]Other acne |
| Myu6F00 | [X]Acne, unspecified |
| Alopecia | |
| 1N02.00 | C/O: hair loss |
| 22D4.00 | O/E - loss of hair |
| 22D7.11 | O/E - alopecia |
| M240.00 | Alopecia |
| M240000 | Alopecia unspecified |
| M240011 | Baldness |
| M240012 | Hair loss |
| M240200 | Male pattern alopecia |
| M240z00 | Alopecia NOS |
| Contraceptive management | |
| 61...00 | Contraception |
| 614..11 | Oral contraception |
| 614..12 | Pill - oral contraception |
| 6145.00 | Oral contraception -no problem |
| 614Z.00 | Oral contraception NOS |
| 61X..00 | Planned contraception method |
| 61Y..00 | Uses contraception |
| 61Z..00 | Contraception NOS |
| 6777.00 | Contraception counselling |
| 6147.00 | Combined oral contraceptive |

| | |
|---------|--|
| 67Ij.00 | Advice to GP to change pt oral contraceptive from combined |
| 1561.00 | H/O: oral contraceptive usage |
| 1561000 | H/O: progestogen only oral contraceptive usage |
| 614..00 | Oral contraceptive |
| 614..11 | Oral contraception |
| 614..12 | Pill - oral contraception |
| 6141.00 | Oral contraceptive started |
| 6142.00 | Oral contraceptive stopped |
| 6143.00 | Oral contraceptive re-started |
| 6144.00 | Oral contraceptive repeat |
| 6145.00 | Oral contraception -no problem |
| 6146.00 | Oral contraception - problem |
| 6146100 | Headache caused by oral contraceptive pill |
| 6146200 | Hypertension induced by oral contraceptive pill |
| 6147.00 | Combined oral contraceptive |
| 6148.00 | Progestagen only oral contraceptive |

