| 6148.11 | Mini-pill: oral contraceptive |
| 6148.13 | Progestogen only oral contraceptive |
| 6149.00 | Oral contraceptive changed |
| 614D.00 | Oral contraceptive prescribed |
| 614E.00 | Oral contraceptive advice |
| 614Z.00 | Oral contraception NOS |
| 61J0.00 | Oral contraceptive pill contraindicated |
| 679a.00 | Education about missed dose of oral contraceptive |
| 67IH.00 | Advice about progestogen only oral contraceptive |
| 1569.00 | H/O: symptothermal method of contraception usage |
| 156B.00 | H/O: withdrawal contraception method usage |
| 1P77.00 | Reason for no contraception |
| 612..00 | Contraception not needed |
| 612Z.00 | Contraception not needed NOS |
| 6146.00 | Oral contraception - problem |
| 614F.00 | Emergency contraception advice |
| 615..11 | Coil contraception |
| 615..12 | IUD contraception |
| 616..11 | CAP contraception |
| 616..12 | Diaphragm contraception |
| 617..11 | Sheath contraception |
| 618..00 | Rhythm method contraception |
| 619..00 | Withdrawal contraception |
| 61A..00 | Post-coital contraception |
| 61AZ.00 | Post-coital contraception NOS |

| | |
|---------|---|
| 61B..11 | Depot contraception |
| 61B5.00 | Depot contraception stopped |
| 61C..11 | Spermicide alone contraception |
| 61E..00 | Sympto-thermal contraception |
| 61FZ.00 | Post-coital contraception NOS |
| 61J0.00 | Oral contraceptive pill contraindicated |
| 679a.00 | Education about missed dose of oral contraceptive |
| 67IH.00 | Advice about progestogen only oral contraceptive |
| 1569.00 | H/O: symptothermal method of contraception usage |
| 156B.00 | H/O: withdrawal contraception method usage |
| 612..00 | Contraception not needed |
| 612Z.00 | Contraception not needed NOS |
| 6146.00 | Oral contraception - problem |
| 614F.00 | Emergency contraception advice |
| 61H..00 | Contraception: female sterilis |
| 61J..00 | Contraception contraindicated |
| 61L..00 | Contraception status unknown |
| 61M..00 | Emergency contraception |
| 61P..00 | No current contraception |
| 61Q..00 | Partner contraception |
| 61R..00 | Intrauterine system contraception |
| 61S..00 | Contraception method not decided |
| 61V..00 | Problem with contraception |
| 679K500 | Education for withdrawal contraception |
| 67P2.00 | Discussion about contraception injection |
| 8CAw.00 | Advice about long acting reversible contraception |
| 8CAw100 | Verbal advice about long acting reversible contraception |

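### Some entries in the THIN code lists do not match what the protocol says they identify: oral products under injections, codes without a start or end role, and negated codes counted as contraceptive management

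*Protocol*

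**What the plan says.** **Exposure list.** Section 9.3 refers to Tables 16.1 and 16.2 for the codes that identify hormonal contraceptives. The second is headed "Table 16.2 Gemscript codes to identify hormonal contraceptives in THIN", although its injection, implant and intra-uterine blocks also contain Read codes. The injection block includes "94485998 | Medroxyprogesterone acetate 80mg/ml Oral suspension", a second code with the same description (94789998), and "61B5.00 | Depot contraception stopped". The implant block includes "9m7..00 | Contraceptive implant removal invitation".

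**Rules applied to that list.** Section 9.3.1 gives injections, implants and intra-uterine devices the label's duration of effectiveness. It shortens this only when removal of a device or implant is recorded. Section 9.3.2 computes concomitant use separately by route, because the validity of estimated durations differs by route.

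**Diagnosis lists.** Section 9.3 aims at hyperandrogenic conditions, or conditions for which oestrogen/progestin combinations are often prescribed. For THIN, Table 16.6 places "612..00 | Contraception not needed" under contraceptive management and "M153000 | Acne rosacea" under acne. For PHARMO and HSD, Table 16.5 gives the ICD-9 codes for menstrual problems as "626.1, 626.2, 626.4, 626.8, 626.9", and the next row reads "Oligomenorrhoea/amenorrhoea | N91 | 626.0, 626.1".

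**The concern.** A code list is the operational definition of exposure or diagnosis. If an entry does not mean what its block says, a programmer who follows the protocol will misclassify the record.

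For Table 16.2 the stake is concomitant use of CPA/EE and other hormonal contraceptives in THIN. This is the main outcome of the 2017 extension and the quantity whose pattern over time the regulator asked to see. In 2014 THIN supplied 2,341 of the 1,401 + 2,341 + 261 = 4,003 new users in Tables 15.1 to 15.3, about 58%.

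For Table 16.6 the stake is the apparent indication for CPA/EE in THIN in 2011, 2012 and 2014. The acne flag also splits the prior-treatment tables (14.5 and 14.6).

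**Working it through.** No figure in the protocol can be reproduced here, since no counts per code are given. The check compares each entry with its block heading and with the rules that use it.

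**1. Oral suspensions under injections (Table 16.2).** The block has eight Gemscript codes: 85241998, 85242998, 94485998, 94789998, 95700998, 97454998, 97920998 and 97921998. Two of the eight are described as oral suspensions. Under Section 9.3.1 anything typed as an injection gets an injection's label duration, and under Section 9.3.2 it is reported in the injection stratum. Both are wrong for an oral product. The oral progestogen block contains no medroxyprogesterone, so nothing in the list suggests that these were meant as oral contraceptives. This error follows directly from the text.

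**2. Codes without a role (Table 16.2).** The Read codes sort as follows by their descriptions:

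| Block | Start or repeat | Current use or unspecified | End | Neither |
|---|---|---|---|---|
| Injections (9) | 3: 61B1.00, 61B1.11, 61B2.00 | 5: 61B..00, 61B..11, 61B3.00, 61B4.00, 61BZ.00 | 1: 61B5.00 | 0 |
| Implants (11) | 3: 61KA.00, 7G2AB00, 7G2AA00 | 5: 61K..00, 61KB.00, 61KD.00, 61KE.00, 61KZ.00 | 2: 7G2H700, 7G2H500 | 1: 9m7..00 |
| Levonorgestrel intra-uterine system (3) | 1: 7E09400 | 1: 615S.00 | 1: 7E09500 | 0 |

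The table therefore mixes roles, and the protocol does not say which code does what. For the three device and implant removal codes, Section 9.3.1 supplies the meaning: they end exposure. For 61B5.00 it supplies none, because its early-end rule does not mention injections. If the code were treated like its neighbours, a woman stopping her injection as she starts CPA/EE would be given a further injection interval. If that interval fell wholly inside her CPA/EE episode, Section 9.3.2 would class it as concomitant. Code 9m7..00 records an invitation, so it marks neither a start nor an end.

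**3. Contraceptive management (Table 16.6).** Besides 612..00 (listed twice, as is 612Z.00), the category includes codes for no current contraception (61P..00), unknown status (61L..00) and contraception being contraindicated (61J..00). It also includes non-hormonal methods: sheath (617..11), diaphragm (616..12), withdrawal (619..00), rhythm (618..00), spermicide (61C..11) and female sterilisation (61H..00). None of these is a condition for which an oestrogen/progestin combination is prescribed, which is the purpose Section 9.3 gives.

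**4. Acne (Table 16.6).** M153000 is the only M15 code in the list. The other M-chapter disease codes are in the M26 sebaceous-gland family. The entry brings rosacea into a flag meant for a hyperandrogenic condition.

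**5. ICD-9 626.1 (Table 16.5).** It appears in two rows. The ICD-10 columns (N92 and N94.3-N94.9 against N91) and the ICPC columns (X02-X03 and X06-X09 against X05) keep those rows apart. PHARMO's GP diagnoses are coded in ICPC (Section 9.4.1), THIN uses Read codes, and the ICD-9 column carries an HSD-specific note. The overlap therefore appears to concern HSD only (495, 446 and 261 starters in 2011, 2012 and 2014).

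**6. Reach.** Section 9.3 limits the extension to demographics and concomitant use. Table 16.2 feeds it; Tables 16.5 and 16.6 do not. Only Table 16.3 is marked as preliminary.

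**The case against.** The strongest reply concerns the stop code. Table 16.2 plainly holds end markers, since it lists removals that Section 9.3.1 uses to end exposure, and 61B5.00 may be intended in the same way. Section 9.3.1 builds episodes from prescriptions and nowhere says that a record of stopping, checking or in-situ status opens a label-long episode. This stands. A reader might infer that each stopped record adds an interval of false use, or that a check restarts a multi-year device clock; the documents do not establish either. A woman with a device recorded in situ is in fact exposed, and calendar-year follow-up is at most 12 months. What remains is that the role is unstated and injections have no end rule. Intended end markers cannot explain the oral suspensions or the removal invitation.

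Second, Section 9.9 already concedes misclassification of long-acting methods in both directions and expects their use to be low. That bears on size. It does not cover errors in the lists themselves.

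Third, the regulator asked for the same methodology as before (Table 5.1, item 6), and an unchanged list applied to every year would keep errors broadly constant. This is a fair reason to show both lists, not to retain entries known to be wrong.

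Fourth, a reader might infer that differences between databases are artefacts of the lists. The footnote to Table 16.5 adds text mining of GP episodes, so neither the size nor the direction of such a difference can be read from the codes, and the objectives compare periods, not databases.

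**Conclusion.** The point holds in limited form. Two kinds of entry are wrong as written: the two oral suspension codes under injections, and the negated, unknown and non-hormonal codes (with rosacea) in the THIN diagnosis list. A third is under-specified: Table 16.2 mixes start, continuing and end codes without saying so, has no rule for a stopped injection, and includes one code that fits no role.

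The documents do not show that concomitant use in THIN is inflated. That conclusion would need counts per code and knowledge of how the stop and check codes were programmed, and neither is given. Nor is 626.1 a wrong diagnosis: the rows of Tables 14.7 and 14.8 are neither declared exclusive nor summed, so a record in two rows inflates no total. It is an inconsistency between coding columns.

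The effect is of unknown size and may be small, given the expected low use of long-acting methods. The Table 16.2 entries matter for the extension; the diagnosis entries matter only for the 2011-2014 tables. Correction is worthwhile because it uses existing data and removes doubt about the outcome on which the trend rests.

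**What to change.** - **Table 16.2:** remove 94485998, 94789998 and 9m7..00 from the long-acting lists. Label each remaining long-acting code as start, current use (shows exposure but does not restart the duration) or end. State in Section 9.3.1 that 61B5.00 ends an injection episode, or at the least never starts one.
- **Table 16.6:** remove the not-needed, none, unknown, contraindicated and non-hormonal method codes from contraceptive management, and M153000 from acne.
- **Table 16.5 (tidy-up):** list ICD-9 626.1 in one row only, in line with the ICD-10 and ICPC columns.
- **Comparability:** apply the corrected Table 16.2 to every THIN year (2011, 2012, 2014 to 2017) and report concomitant use once under the old and once under the new list.

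The cost is a code-list edit, one added rule and a re-run of the earlier THIN years. No new data are needed. The THIN cohort sizes do not change, because Section 9.2 selects new users on CPA/EE codes, which are untouched.

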| 8CAw200 | Written advice about long acting reversible contraception |
| 8CED.00 | Emergency contraception leaflet given |
| 8CEE.00 | Contraception leaflet given |
| 8CEF.00 | Intrauterine device contraception leaflet given |
| 8CEG.00 | Long acting reversible contraception leaflet given |
| 961..11 | FP1001 - contraception claim |
| 98CA.00 | GMS4 claim - contraception (non IUCD) signed |
| 98CB.00 | GMS4 claim - contraception (non IUCD) sent to HA |
| 98CC.00 | GMS4 claim - contraception (non IUCD) up to date |
| 98CD.00 | GMS4 claim - contraception (non IUCD) due |
| 98CE.00 | GMS4 claim - contraception (non IUCD) due next visit |
| 98CF.00 | GMS4 claim - contraception (non IUCD) cancelled |
| 98CG.00 | GMS4 claim - contraception (non IUCD) not claimed |
| 98CH.00 | GMS4 claim - contraception (non IUCD) forgot to claim |

| | |
|---------------------------|---|
| 98CI.00 | GMS4 claim - contraception (non IUCD) paid |
| 98CJ.00 | GMS4 claim - contraception (non IUCD) returned unpaid |
| 98CK.00 | GMS4 claim - contraception (IUCD) signed |
| 98CL.00 | GMS4 claim - contraception (IUCD) sent to HA |
| 98CM.00 | GMS4 claim - contraception (IUCD) due with new IUCD |
| 98CN.00 | GMS4 claim - contraception (IUCD) paid |
| SP03217 | Contraception IUCD causing bleeding |
| ZV15700 | [V]Personal history of contraception |
| Hirsutism | |
| M241.00 | Hirsutism - hypertrichosis |
| M241.11 | Polytrichia |
| M241100 | Idiopathic hypertrichosis |
| M241200 | Hypertrichosis lanuginosa (acquired) |
| M241400 | Hypertrichosis partialis |
| M241500 | Hypertrichosis universalis |
| M241600 | Polytrichia |
| M241z00 | Hypertrichosis NOS |
| Menstrual problems | |
| K584.00 | Premenstrual tension syndrome |
| K584.11 | Migraine - menstrual |
| 1573.11 | H/O: heavy periods |
| K592.00 | Excessive or frequent menstruation |
| K592.11 | Frequent menses |
| K592.12 | Hypermenorrhoea |
| K592000 | Menorrhagia |
| K592011 | Heavy periods |
| K592100 | Polymenorrhoea |
| K592111 | Epimenorrhoea |
| K592z00 | Excessive or frequent menstruation NOS |
| K593.00 | Puberty bleeding |
| K593.11 | Pubertal bleeding and menorrhagia |
| K595.00 | Ovulation bleeding |
| K595.11 | Intermenstrual bleeding - regular |
| K596.00 | Metrorrhagia |
| K596.11 | Intermenstrual bleeding - irregular |
| K598.00 | Menometrorrhagia |
| K599.00 | Mid-cycle bleeding |
| K59y.11 | Metropathia haemorrhagica |
| K59yx00 | Dysfunctional uterine haemorrhage NOS |
| K59yx11 | Dysfunctional uterine bleeding |

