| K59yy00 | Functional uterine haemorrhage NOS |

| | |
|-----------------------------|--|
| K59z.11 | Break - through bleeding |
| 1574.00 | H/O: dysmenorrhoea |
| Eu45y11 | [X]Psychogenic dysmenorrhoea |
| K582.00 | Mittelschmerz - ovulation pain |
| K583.00 | Dysmenorrhoea |
| K583.11 | Painful menorrhoea |
| K583.12 | Painful menstruation |
| K583.13 | Period pains |
| K583.14 | Spasmodic dysmenorrhoea |
| K583000 | Primary dysmenorrhoea |
| K583100 | Secondary dysmenorrhoea |
| 1572.00 | H/O: polymenorrhoea |
| 158..00 | H/O: abnormal uterine bleeding |
| 158..12 | Vaginal bleeding |
| K56y111 | Bleeding - vaginal NOS |
| K56y112 | BPV - Vaginal bleeding |
| K592.11 | Frequent menses |
| K59y300 | Intermenstrual bleeding |
| K594.00 | Irregular menstrual cycle |
| K594000 | Delayed period |
| K594011 | Late period |
| K594z00 | Irregular menstrual cycle NOS |
| 1573.00 | H/O: menorrhagia |
| K5A0.00 | Premenopausal menorrhagia |
| K5A0.11 | Climacteric menorrhagia |
| K5A6.00 | Perimenopausal menorrhagia |
| 158..00 | H/O: abnormal uterine bleeding |
| 1584.00 | Heavy episode of vaginal bleeding |
| K592.00 | Excessive or frequent menstruation |
| K592z00 | Excessive or frequent menstruation NOS |
| K59y.00 | Other menstruation disorders |
| K59yz00 | Other menstruation disorder NOS |
| K592000 | Menorrhagia |
| K59y000 | Retained menstruation |
| K594012 | Delayed menstruation |
| Oligomenorrhoea/amenorrhoea | |
| 1571.00 | H/O: amenorrhoea |
| K590.00 | Absence of menstruation |
| K590.11 | Amenorrhoea |
| K590000 | Primary amenorrhoea |
| K590100 | Secondary amenorrhoea |
| K590111 | Post-pill amenorrhoea |

| | |
|------------|---------------------------------------|
| K590z00 | Amenorrhoea NOS |
| K591.00 | Scanty or infrequent menstruation |
| K591.11 | Infrequent menstruation |
| K59y100 | Suppression of menstruation |
| 1571.00 | H/O: amenorrhoea |
| K590.00 | Absence of menstruation |
| K590111 | Post-pill amenorrhoea |
| K591000 | Hypomenorrhoea |
| K591100 | Oligomenorrhoea |
| K591200 | Primary oligomenorrhoea |
| K591300 | Secondary oligomenorrhoea |
| K591z00 | Scanty or infrequent menstruation NOS |
| PCOS | |
| C164.00 | Polycystic ovaries |
| C164.11 | Isosexual virilisation |
| C164.12 | Stein - Leventhal syndrome |
| C164.13 | Multicystic ovaries |
| C165.00 | Polycystic ovarian syndrome |
| C16y.00 | Other ovarian dysfunction |
| Seborrhoea | |
| M263.00 | Seborrhoea |
| M263000 | Seborrhoea corporis |

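### The ICD-9 (HSD) code list for menstrual problems differs in content from the ICD-10, ICPC and THIN lists, so that row is not like-for-like across the three databases

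*Protocol*

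**What the plan says.** Annex 3, Table 16.5, is headed "Codes of diagnoses of hyperandrogenic conditions during the year before index date for PHARMO and HSD". For menstrual problems it gives three cells that are meant to define the same thing:

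- ICD-10: "N92, N94.3-N94.9"
- ICD-9(-CM): "626.1, 626.2, 626.4, 626.8, 626.9"
- ICPC: "X02-X03, X06-X09"

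The next row, oligomenorrhoea/amenorrhoea, has ICD-10 N91, ICD-9 626.0 and 626.1, and ICPC X05. A footnote to the table says that the diagnoses also draw on text mining of GP episodes.

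Table 16.6 gives the THIN list. Under menstrual problems it includes "K584.00 | Premenstrual tension syndrome" and "K583.00 | Dysmenorrhoea", further pain codes such as "Primary dysmenorrhoea", and puberty bleeding, ovulation bleeding and metrorrhagia.

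The row is reported in Tables 14.7 and 14.8 with PHARMO, THIN and HSD in adjacent columns. Section 9.7 makes the analysis descriptive.

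**The concern.** Section 9.3 includes menstrual problems among the prior diagnoses because oestrogen/progestin combinations are often prescribed for conditions of this kind. Section 9.9 adds that the indication has to be read from recorded diagnoses. The row is thus part of the evidence on why women start CPA/EE.

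If the HSD list covers different complaints from the PHARMO and THIN lists, a reader of Table 14.8 who compares Italy with the UK or the Netherlands will take part of a code-list difference for a difference in prescribing. There are two mismatches. The ICD-9 cell leaves out content that the other lists carry, and it takes in a code that the protocol also assigns to the neighbouring row.

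**Working it through.** The protocol states no figure for this row, so there is nothing to reproduce. The check compares the lists and then asks which way the mismatch pushes the HSD percentage.

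**1. Which list is HSD's.** The HSD sections (9.4.3 and 9.6.3) do not name a diagnosis coding system. Table 16.5 serves PHARMO and HSD. Its hirsutism entry carries an HSD sub-code note inside the ICD-9 column, and section 9.4.1 says PHARMO GP diagnoses are coded in ICPC. Reading ICD-9 as the HSD column is an inference, but a firm one.

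**2. The lists side by side (menstrual problems).**

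| List | Content | Code shared with the oligomenorrhoea/amenorrhoea row? |
|---|---|---|
| ICD-10 | N92 and N94.3-N94.9 | No (that row is N91) |
| ICPC | X02-X03 and X06-X09 | No (that row is X05) |
| THIN | 53 distinct Read codes, 12 of them pain or premenstrual | No (oligomenorrhoea sits under K591) |
| ICD-9 | Five codes, all in category 626 | Yes (626.1) |

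The 12 THIN codes are K584.00, K584.11, 1574.00, Eu45y11, K582.00, K583.00, K583.11 to K583.14, K583000 and K583100.

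The ICD-9 cell stays in one category and shows no counterpart to the N94 block. It also skips codes within 626, while THIN names puberty bleeding, ovulation bleeding and metrorrhagia. The protocol prints descriptors only for THIN. Which ICD-9-CM codes correspond is a matter of the coding system, and the HSD partner must confirm it.

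**3. Direction.** Let T be the prevalence under the wider definition, s the share of those women identifiable only through the missing codes, r the fraction of them recovered by text mining, and o the percentage points of women who enter only through 626.1. Then

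HSD row = T × (1 − s × (1 − r)) + o,

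and the row is too low only if T × s × (1 − r) > o. None of the four quantities is in the documents; all values below are assumptions. The denominators, 495 (2011) and 261 (2014), are from Table 15.3.

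| T | o | r | s = 10% | s = 30% | s = 50% |
|---|---|---|---|---|---|
| 10% | 0 | 0 | 9.0% | 7.0% | 5.0% |
| 10% | 0 | 50% | 9.5% | 8.5% | 7.5% |
| 10% | 0 | 100% | 10.0% | 10.0% | 10.0% |
| 10% | 2 points | 0 | 11.0% | 9.0% | 7.0% |
| 10% | 2 points | 50% | 11.5% | 10.5% | 9.5% |
| 5% | 2 points | 0 | 6.5% | 5.5% | 4.5% |

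The first line corresponds to about 5, 15 and 25 fewer women of 495 (for example 495 × 0.03 = 14.9), and about 3, 8 and 13 fewer of 261.

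With T = 10%, o = 2 points and no recovery, the break-even is s = 0.02 / 0.10 = 20%: the row is too high below that share and too low above it. With half recovered it moves to 0.02 / (0.10 × 0.5) = 40%.

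The omission alone can only lower the row, 626.1 alone can only raise it, and the sum can fall on either side.

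**The case against.** The strongest reply is the table's own footnote. If HSD episodes are text-mined, the code list is not the only route into the row, and section 9.6.3 confirms that HSD has free text. This stands in part. Mining is described as an addition to the codes, the word episode may describe PHARMO records only, and nothing says HSD text is searched for these complaints. The footnote leaves the size open but does not make the lists equal.

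A reader might infer more: that the HSD row is certainly too low, that women with menstrual pain drop out of it, and that non-acne reasons will look rarer in Italy. The documents do not support this. Text mining may recover some of these women, a woman who also has a listed bleeding code stays in the row, and 626.1 pulls the percentage up. Nor can 12 of 53 Read codes (23%) be read as a share of women, because a count of codes says nothing about how often each is recorded. The HSD cohort sizes are denominators, not numbers of women misclassified.

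It is also fair to say that the stakes are low. The row is one of eight descriptive rows. The secondary objective in section 8.1 compares periods, not countries, and a list held constant within HSD does not by itself distort the comparison of 2011/2012 with 2014. Section 9.9 already warns of under-recorded diagnoses. That warning concerns what GPs record, however, not a row defined differently by database.

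**Conclusion.** The point holds as one of comparability. The ICD-9 cell lacks a counterpart to content that the ICD-10 and THIN lists include for the same row, and it lists 626.1 in two rows where the other lists keep oligomenorrhoea separate. The HSD figure in Tables 14.7 and 14.8 is therefore not like-for-like with PHARMO and THIN. Under-capture of menstrual-pain and premenstrual complaints in HSD is probable unless text mining covers HSD, but the net direction and size cannot be fixed from the documents.

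This rests on HSD using the ICD-9 column and on the usual meaning of codes for which the protocol prints no descriptors. The impact is minor: one descriptive row. The 2015-2017 extension does not assess diagnoses (section 9.3) and is unaffected.

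**What to change.** 1. Align the ICD-9 cell in Table 16.5 with the ICD-10, ICPC and THIN content. The HSD partner should confirm the matching ICD-9-CM codes, including those for premenstrual tension, dysmenorrhoea, puberty bleeding, ovulation bleeding and metrorrhagia.
2. Keep 626.1 in the oligomenorrhoea/amenorrhoea row only.
3. State in the footnote whether text mining is applied to HSD.
4. Re-run the HSD row for 2011, 2012 and 2014. If those results are not to be reopened (Table 6.1 planned that final report for March 2016), footnote the row as not comparable with PHARMO and THIN.

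The cost is one code-list edit, one sentence in the footnote and one HSD query, or a table note in place of the query. PHARMO and THIN need no change.
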